The proposed study is a single blinded, randomized study to determine if a targeted balance exercise program improves fall risk in patients with MetS and autonomic neuropathy. Subjects will be defined for entry as having the MetS and autonomic neuropathy but will not be required to have a history of falls. Fall risk will be determined in the study. Following baseline testing participants will be randomized to either a balance exercise program or standard care. Participants in the balance exercise program will be seen weekly to promote program adherence. Standard care participants receive information about fall safety and [will be seen weekly for health education classes] but do not receive tailored exercise instructions.

Participants

Participants aged [50 to 70 years] will be entered based on the presence of MetS and autonomic neuropathy. MetS is defined based on criteria published by the International Diabetes Federation (45).

Subjects must have both MetS and autonomic neuropathy as determined by the study physicians.

A) MetS will be defined based on the 2006 International Diabetes Federation definition (45): Study participants must have central obesity (defined as waist circumference ≥ 94 cm for Europid men and ≥ 80 cm for Europid women, with ethnicity specific values for other groups or if BMI is $> 30\text{kg}/\text{m}^2$ central obesity can be assumed and waist circumference does not need to be measured) plus any two of the following four factors: (1) raised triglyceride level (≥ 150 mg/dL) or specific treatment for this lipid abnormality, (2) reduced HDL cholesterol (< 40 mg/dL in males and < 50 mg/dL in females) or specific treatment for this lipid abnormality, (3) raised BP (systolic BP ≥ 130 mm Hg or diastolic BP ≥ 85 mm Hg) or treatment of previously diagnosed hypertension, or (4) raised fasting plasma glucose ≥ 100 mg/dL or previously diagnosed type 2 diabetes.

B) Autonomic peripheral neuropathy will be defined according to the Toronto Diabetic Neuropathy

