At screening the potential study participants will be evaluated for MetS and autonomic neuropathy. Subjects may be enrolled if they have MetS as defined under the participants and an abnormal SAS or two abnormal autonomic function tests as defined under participants. Blood samples to confirm the presence of MetS will be drawn (2hr OGTT, lipid profile). *If the screening fasting glucose is ≥ 126 (subject is diabetic), then for safety, the rest of the OGTT will be deferred.* SAS and autonomic studies will determine if autonomic neuropathy is present (required for enrollment). Randomization assignments will be provided by the study statistician once the subject has completed the screening visit.

During screening or at anytime during enrollment in the study, if participants are found to have under or untreated hypertension or hyperlipidemia the abnormal results of clinical tests will be sent to the participant's primary care physicians for further evaluation.

Randomization Scheme

Randomization will occur at the time of enrollment. Participants will have an equal chance of being assigned to either study group. Due to concerns regarding recruitment we do not feel that only including

individuals with a history of falls in the study sample would be practical. On the other hand only including those without a history of falls may decrease the sensitivity of the study. Therefore, a stratified randomization will be utilized to achieve between group comparability in terms of the numbers of fallers and nonfallers in each group. This will be especially important due to the relatively small total sample size. Within each stratum a blocked randomization strategy will be used to ensure an equal number of participants in each group during the course of randomization. Because the trial is not double blind the blocking factor will be varied between 2 and 4 as recruitment continues so that the blocking factor remains unpredictable to study staff. Blocked randomization can increase the power of a study but will require appropriate statistical analysis since simple randomization will not be used.

Table 2. Testing Scheme for Subjects Screened and Enrolled in the Study

	Screening	Enrollment	12 weeks	24 weeks
hCG (females of child bearing potential only)	X			
Physical and neurologic examination	X		X	X
Waist Circumference	X		X	X
BP measurement			X	X
Metabolic blood tests (OGTT, lipids)	X		X	X
Autonomic studies and SAS questionnaire	X		X	X
FSST & DGI		X	X	X
ABC Survey		X	X	X

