determine if any of them are potential effect modifiers or confounders. [The unadjusted associations between covariates and the primary outcome variable will first be examined. The covariates that are found to have statistically significant associations with both the exposure and the outcome variables will be examined by stratified analysis to determine if they are potential confounders. All covariates will be examined by stratified analysis to determine if they are potential effect modifiers. If there are potential effect modifiers, interaction terms will be included in the logistic regression model. If the interaction terms are found to be significant in the model, indicating that there is effect modification, then the final analysis will be stratified].

An intention to treat analysis will be used. Descriptive statistics will be used to assess the distribution of the FSST. Bivariate analysis including Chi-square and t-tests to compare the categorical and continuous variables will be performed. Mean and standard deviation for the FSST at each time point will be computed and analysis of variance will be used to compare the means of the two treatment groups, controlling for baseline characteristics. The main hypothesis is that the participants in the balance exercise program will show a greater improvement in the FSST at 12 weeks compared to baseline than the participants in the standard care group.

Table 4. Hypothesis Testing Plan

Endpoints	Baseline	12 weeks
Primary	FSST	FSST
Secondary	Instrumented DGI (time spent in double support)	Instrumented DGI (time spent in double support)
Tertiary	ABC scale	ABC scale
Exploratory 1	ActiveStep (recovery steps)	ActiveStep (recovery steps)
Exploratory 3	Autonomic testing	

[Primary hypothesis] – the change in FSST from baseline to 12 weeks will be compared between the standard care and exercise intervention groups to determine if there is a significantly significant difference between the two groups. (covariates included in the model will include outcome at baseline, gender, age, race, and intervention group)

Secondary hypothesis – the change in the DGI score and time spent in double support on the instrumented DGI from baseline to 12 weeks will be compared between the standard care and exercise intervention groups to determine if there is a statistically significant difference between the two groups.

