Tertiary hypothesis – the change in the score on the ABC scale from baseline to 12 weeks will be compared between the standard care and exercise intervention groups to determine if there is a statistically significant difference between the two groups.

Exploratory hypothesis 1 – the change in the number of recovery steps taken on the ActiveStep from baseline to 12 weeks will be compared between the standard care and exercise intervention groups to determine if there is a statistically significant difference between the two groups.

Exploratory hypothesis 2 – the individual results of autonomic testing (30:15 ratio, valsalva ratio, E:I ratio, blood pressure response to valsalva and tilt table testing) as well as the cardiovagal and adrenergic subscores on the CASS will be compared between those with and without a history of falls at baseline to determine if there is a statistically significant difference between the two groups.

Upon enrollment participants will be randomized using a stratified randomization to achieve group comparability in term of the number of fallers and nonfallers in each group. Due to the fact that randomization will be stratified the analysis will also be stratified and the adjusted analysis will include not only the covariates that are found to be different between the groups, but also those stratified during randomization (4)].

A secondary analysis to examine the individuals that received the full dose of the intervention compared with those that only receive some of them will be done with the understanding that per protocol analyses are not as trustworthy as intention to treat analysis and will not be the preferred analysis (77). [In an attempt to examine the effects of the number of sessions attended we will to add a model that includes the number of sessions attended to the exploratory analyses].

Recruitment

There is a specific weekly neuromuscular clinic at the Baltimore VA as well as daily neurology clinics. Approximately 15-20 veterans with MetS are seen each week. We will also recruit subjects through the Baltimore GRECC utilizing subjects referred to the MOVE program and through the GRECC recruitment core. Further strategies that we have used are web advertising through clinical trials.gov, VA and University of

Maryland websites, and mass faxing of trial information to primary care physicians and neurologists in the greater Baltimore metropolitan area.

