The network incorporates patient groups, local neurology and primary care practices, regional community and specialty hospitals, and VA clinics and hospitals that directly interact with neuromuscular clinics.

Advancing Science System (COMPASS) to recruit subjects for clinical research and establish a volunteer registry. COMPASS provides UM researchers with a search-and-discovery tool to identify potential study participants. These methods have been successful in current and previous trials the PI is conducting. In combination, we are confident that the recruitment goals can be met.

Measurements in subjects:

Measures of Fall Risk:

1) Four Square Step Test (FSST): The FSST involves the participant stepping over four canes that are laid on the ground at 90° angles to each other. A cross is formed on the floor by the four canes (90cm long) resting flat on the floor. The participant stands in one of the squares (square 1) formed by the canes facing forward. They are then instructed to step as quickly as possible into each square in a specified sequence; rotating clockwise around the “plus sign” by moving forward to the right, backward, and to the left. They then reverse their direction and move in a counterclockwise direction (14). The score is recorded as the time taken to complete the sequence. Two FSSTs are completed and the best time is taken as the score.

A cutoff score of greater than 15 seconds on the FSST has been identified to categorize subjects as multiple fallers. This cutoff score has a positive predictive value of 86% and a negative predictive value of 94% in a population of community dwelling older adults. The FSST was found to have a higher combined sensitivity and specificity than the Timed Up and Go test, Step Test, and Functional Reach Test in this patient population (14).

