2) Quantitative Sudomotor Axon Reflex Test (QSART): is based upon the axon reflex sweat response mediated by the postganglionic sympathetic sudomotor axons that are activated by acetylcholine (85, 86). The stimulus is a constant electrical current applied for five minutes and then the sweat response is recorded for a subsequent five minutes. The total sweat volume and the sweat onset latency are recorded at 4 sites: the forearm, proximal leg, distal leg and foot. Results are converted to percentiles and then to standard normal deviate.

3) Tilt Table Testing: A 70 degree 5 minute upright tilt will be performed on each subject as previously described (32, 84, 85). The tilt table provides a measurement of baroreflex sensitivity and orthostatic response that is important in understanding autonomic balance in subjects with autonomic neuropathy. Heart rate and beat to BP variation will be monitored during the complete study. Any orthostatic symptoms will be recorded during the study. At the end of the study, the patient will be returned to the supine position.

4) Composite Autonomic Scoring Scale (CASS): A composite score of autonomic function will be used to assess autonomic neuropathy. The 10 point CASS score assesses the following: QSART, orthostatic BP, heart rate response to tilt, heart rate response to deep breathing, the valsalva ratio, and beat-to-beat BP measurements during phases II and IV of the Valsalva maneuver, tilt, and deep breathing (87, 88). The CASS provides a total score and also autonomic subcomponents. One of these subcomponents requires measurement of the tilt table response.

5) Survey of Autonomic Symptoms (SAS): This is a questionnaire designed to assess symptoms of peripheral autonomic function and determines both the number of positive symptoms as well as the frequency of the symptoms and determines scores for each. The scale has been validated in patients with diabetic neuropathy against other autonomic scales and autonomic testing (32).

Intervention Programs

Once they have been enrolled in the study, participants will be randomized to either a balance exercise program or receive standard care. Both groups will receive education regarding falls and falls prevention and will be contacted on a weekly basis from members of the study staff. However, participants in the balance exercise program will be instructed in a personalized balance exercise program.

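### Could the treatment arm be assigned before the baseline Four Square Step Test is recorded?

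*Combined protocol and SAP*

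**What the plan says.** Five statements in the combined protocol and SAP bear on when participants are allocated.

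- Research Design and Methods, opening paragraph: "Following baseline testing participants will be randomized to either a balance exercise program or standard care".
- Screening, last sentence of the first paragraph: "Randomization assignments will be provided by the study statistician once the subject has completed the screening visit".
- Randomization Scheme, first sentence: "Randomization will occur at the time of enrollment".
- Statistical Analyses, on stratification: "Upon enrollment participants will be randomized using a stratified randomization to achieve group comparability".
- Intervention Programs, first sentence: "Once they have been enrolled in the study, participants will be randomized to either a balance exercise program or receive standard care".

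Table 2 has separate Screening and Enrollment columns. The FSST, the Dynamic Gait Index (DGI) and the ABC survey have no mark under Screening and are first marked under Enrollment. The payment terms under Intervention Programs also list screening and enrollment as separate visits.

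For the primary hypothesis, "the change in FSST from baseline to 12 weeks will be compared between the standard care and exercise intervention groups", and the "covariates included in the model will include outcome at baseline, gender, age, race, and intervention group". The Blinding and Unblinding Plan says that participants know their arm, that outcome assessors do not, and that only the research assistant and the biostatistician handle the randomization list.

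**The concern.** The Screening sentence links release of the assignment to the end of a visit at which no FSST is done. Someone working from that paragraph alone could obtain the arm, tell the participant, and only then run the baseline tests at the Enrollment visit. Nothing in the mechanics of randomization would prevent this, because the stratifier is fall history, which does not depend on the FSST.

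The stake is the status of the baseline. In the FSST, participants are timed, and "They are then instructed to step as quickly as possible into each square in a specified sequence", so the score depends on effort. A participant who already knows the arm might try harder or less hard. Baseline FSST is both the starting point of the primary change score and a covariate in the primary model. It is also among the variables used to check that the groups are comparable. All three uses presume a value that the allocation cannot have influenced. Blinded assessors and standardized instructions limit the assessor's influence but not the participant's effort. The blinding section describes the blinded assessments relative to the intervention, not relative to allocation, so it does not settle the order.

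**Working it through.** The plan gives no figure to reproduce on this point. The check is whether the five statements conflict, followed by a small calculation of scale.

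**Step 1: candidate sequences.**

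- A: screening; baseline tests at the Enrollment visit; randomization at that visit.
- B: screening; assignment issued; Enrollment visit with baseline tests.
- C: screening; randomization at the start of the Enrollment visit; baseline tests later in that visit.

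**Step 2: each statement against each sequence**, taking enrollment to mean the visit shown in Table 2.

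| Statement | A | B | C |
|---|---|---|---|
| Research Design and Methods (after baseline testing) | fits | excluded | excluded |
| Screening (once screening is complete) | fits | fits | fits |
| Randomization Scheme (at enrollment) | fits | does not fit | fits |
| Statistical Analyses (upon enrollment) | fits | does not fit | fits |
| Intervention Programs (after enrollment) | fits | does not fit | fits |
| Statements satisfied | 5 of 5 | 1 of 5 | 4 of 5 |

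Only A satisfies all five. If enrollment were instead read as a status gained when eligibility is confirmed, B would sit better with the last three rows, but the first row would still exclude it. The first row alone therefore decides the order, and it is explicit.

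**Step 3: the Screening sentence.** It says that the assignment is not available until screening is complete. It does not say that the assignment is issued before the Enrollment visit. It closes a paragraph about eligibility, where the natural message is that nobody is allocated before qualifying. The subsection that follows gives the time of randomization. An earliest point and a later actual time are compatible.

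**Step 4: scale if the order were broken.** Let d be an arm-related shift in one arm's observed baseline FSST, with the 12-week value unaffected. Write X for baseline, Y for 12 weeks, and subscripts 1 and 0 for the arms.

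- Unadjusted difference in change: (Y1 − X1) − (Y0 − X0). Raising X1 by d moves it by −d.
- Baseline-adjusted difference: (Y1 − Y0) − b(X1 − X0). It moves by −b·d, where b is the slope of the 12-week value on baseline. Using change as the outcome, with baseline as a covariate, gives the same treatment estimate.

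The 2.0 s design difference comes from Sample Size Calculation. Take d = 0.1 s purely as a unit, and b from 0.3 to 0.9 as an assumed range, since the documents give no slope:

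- unadjusted: 0.1 / 2.0 = 5% of the design difference;
- adjusted, b = 0.3: 0.3 × 0.1 = 0.03 s, and 0.03 / 2.0 = 1.5%;
- adjusted, b = 0.9: 0.9 × 0.1 = 0.09 s, and 0.09 / 2.0 = 4.5%.

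These figures say how a shift would carry through. They do not say that one would occur. Under sequence A, d = 0 for knowledge of the arm, and every line is zero.

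**The case for a change.** The best argument for a change is that the explicit ordering appears once, in a design overview, while the looser sentence sits in the operational section that site staff would consult. The three enrollment statements do not order the FSST against allocation within the visit, so sequence C is ruled out by that single overview sentence. No section says when participants are told their arm, and the orientation meeting under Standard Care has no date. A baseline taken after allocation cannot be repaired later, and covariate adjustment would shrink such a shift without removing it. A clarifying sentence would cost almost nothing.

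Most of this is accurate, and the Screening sentence could have been clearer. It does not amount to a fault in the plan. One unambiguous statement is enough when no other statement contradicts it. For harm to follow, staff would have to set that statement aside, participants would have to learn their arm before the baseline FSST, and that knowledge would have to change effort differently in the two arms. The documents support none of these steps. The schematic of screening, enrollment and follow-up (Fig. 7) is not visible in this copy and may show the order, so it cannot be said that the order is given only once. Participants also know their arm at the 12-week test whatever happens at baseline, so rewording would not remove effort effects from the primary comparison.

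**Conclusion.** The concern does not call for a change. The wording is loose in one of five places, the five statements are compatible, and the one that addresses the order directly puts baseline testing before randomization. Followed as written, the plan yields a baseline FSST recorded before allocation, and the change score, the covariate and the baseline comparison all keep their meaning. New text would only repeat an order that the plan already gives.

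The effect on the primary result is nil under the stated order. The 5% (unadjusted) and 1.5% to 4.5% (adjusted) figures per 0.1 s are arbitrary units of scale and not estimates for this trial.

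The conclusion rests on three assumptions: that staff treat the statement in Research Design and Methods as binding, that baseline testing there includes the FSST (Table 4 lists it under Baseline), and that Fig. 7 does not show a different order. If trial records showed arms disclosed before baseline testing, that would be a departure from the protocol and would need its own assessment.

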Sample Size Calculation

The FSST was chosen as the primary efficacy measure because it has been demonstrated to be a reliable and valid clinical test of fall risk. Importantly, it has been shown to have a higher sensitivity and specificity than the Timed Up and Go test, the Step Test and the Functional Reach Test for identifying differences between groups of older adults; non-fallers, non-multiple fallers, and multiple fallers (14). In normal controls the FSST has been shown to have a standard deviation of 2.34 seconds (74). A minimal detectable change has not been established in a population of elderly adults who are at risk for falls. However, in other populations of patients with neurological disorders that had a similar age and mean score at baseline the minimal detectable change estimate for the FSST was 4.6 seconds (75).

Table 3. Number of Subjects Required for a Range of Mean Differences in FSST

Smallest detectable mean difference in FSST (SD=2.34)	Number of subjects per group	Actual Power
1.0	87	0.800
1.5	40	0.808
2.0	23	0.809
3.0	11	0.816
4.0	7	0.835

Sample size per group required for to detect a specified mean difference in FSST at 12 weeks based on a two sample t test, power=0.8, significance level=0.05

Based on the FSST, the required sample size to detect a difference of 2.0 seconds is 23 participants per group. Based on results from similar intervention studies, the drop-out rate is up to 25% (14, 76). Allowing for a 10% drop-out rate in the standard care group, we will need to recruit 26 participants into the standard care group and 29 participants into the balance exercise group for a total of 55 participants.

Statistical Analyses

The two treatment groups will be compared using baseline demographic variables (age and gender) and relevant prognostic covariants (history of falls, BMI, abdominal circumference, fasting glucose, BP, lipids, SAS score, and baseline values of primary endpoints). These variables will be tested for baseline comparability using a univariate analysis. The variables will also be examined by stratified analysis to

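### A significant interaction with any of ten or more covariates could replace the primary FSST model with a stratified analysis, and the plan does not say which result then decides

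*Combined protocol and SAP*

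**What the plan says.** All of this is in the Statistical Analyses section unless noted.

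- **Candidates.** Age and gender are listed, followed by "relevant prognostic covariants (history of falls, BMI, abdominal circumference, fasting glucose, BP, lipids, SAS score, and baseline values of primary endpoints". That is 2 + 8 = 10 items, and more if blood pressure and lipids are split into components or race is added.
- **Search.** "All covariates will be examined by stratified analysis to determine if they are potential effect modifiers". Where potential modifiers are found, "interaction terms will be included in the logistic regression model".
- **Switch.** If the "interaction terms are found to be significant in the model, indicating that there is effect modification, then the final analysis will be stratified".
- **Primary model.** For the change in FSST from baseline to 12 weeks, "covariates included in the model will include outcome at baseline, gender, age, race, and intervention group".
- **Further adjustment.** A later paragraph says that "the adjusted analysis will include not only the covariates that are found to be different between the groups", "but also those stratified during randomization". Fall history is the randomisation stratum. On baseline differences the plan says: "These variables will be tested for baseline comparability using a univariate analysis".

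The only significance level given is the 0.05 in the note to the sample-size table. The only remark on repeated testing, in the Data and Safety Monitoring Plan, concerns interim looks.

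**The concern.** The switch sentence governs the final analysis and is not labelled exploratory, so it can displace the primary model named in the same section. Several things that would make it a usable rule are missing:

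- what makes a covariate a potential modifier, and where continuous covariates are cut;
- whether interaction terms are tested singly or jointly, and whether one significant term is enough;
- any control for the number of tests;
- whether, after a switch, one estimate pooled over strata or the separate stratum results decide the hypothesis.

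Two things are at stake. The first is type I error, but only if a stratum result can carry a claim. The second arises even when the programme works equally in everyone: splitting 46 people because their halves happen to differ tends to produce an apparent benefit in one half only. The trial is a pilot meant to inform a larger one, so that message could affect whom the next trial targets.

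**Working it through.** **Step 1. The plan's own figure.** Inputs from Sample Size Calculation: difference 2.0 s, SD 2.34 s, 23 per group, significance level 0.05 (taken as two-sided, which reproduces the table). For a two-sample t test the noncentrality is (2.0/2.34) × √(n/2) on 2n − 2 degrees of freedom.

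- n = 23: 0.855 × √11.5 = 2.90, 44 df, power 0.809. This matches the table.
- n = 12: 0.855 × √6 = 2.09, 22 df, power 0.517.
- n = 11: 0.855 × √5.5 = 2.00, 20 df, power 0.479.

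A half-size stratum therefore has power of about 0.48-0.52. If the split were on fall history at the pilot rate (9 of 44, 20.45%), the faller stratum would hold about 23 × 0.2045 = 4.7, say 5 per arm, with power 0.222.

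**Step 2. Chance of a false trigger.** For k independent tests at 0.05 it is 1 − 0.95^k. For k = 10: 1 − 0.599 = 0.401. For k = 11 (race added) it is 0.431, and for k = 12 it is 0.460.

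**Step 3. Simulation with no treatment effect and no effect modification.** There were 46 completers (2 × 23), 10 covariates, 3,000 runs per cell and 18 cells. Assumptions not in the documents:

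- correlation of baseline with 12-week FSST 0.3, 0.5 or 0.7;
- pairwise covariate correlation 0, 0.3 or 0.6;
- covariates split at the median, or fall history and gender split at 9 of 46;
- after a switch, stratification on the most significant term.

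The fixed ANCOVA (arm, baseline, fall history, gender, age; race not simulated) had type I error 4.5-5.8%. Ranges below run across cells; the 11-20% entry also covers a repeat simulation.

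| Reading of the trigger | Switch fires | Type I error: pooled stratum-adjusted estimate decides | Either stratum may support a claim | Same, Bonferroni over two strata |
|---|---|---|---|---|
| One covariate at a time | 31-41% | 4-6% | 23-30% | 17-20% |
| Screen at p<0.10, then any p<0.05 | 16-37% | 4-6% | 15-27% | 11-19% |
| Any term in one joint model | 31-36% | 4-6% | 11-20% | 9-13% |
| Single joint test | 4-5% | 4-6% | 6-8% | 6-7% |

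**Step 4. Simulation with a uniform 2.0 s benefit** (SD 2.34, median splits, 2,000 runs per cell, 9 cells).

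- The fixed ANCOVA on arm and baseline has power 0.84-0.98.
- One at a time, 31-41% of trials still switch. Of those, 81-96% are significant in exactly one stratum, 3-19% in both and 0-2% in neither.
- With any term in a joint model (a smaller run, 800 replicates per cell, 4 cells), 60-84% of switched trials are significant in exactly one stratum.
- If a pooled stratum-adjusted estimate is used after the switch, power stays at 0.83-0.98.

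Two strata with power near 0.5 would split one-and-one in about 2 × 0.5 × 0.5 = 50% of trials. Selecting trials because their strata differ pushes the share higher.

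**Step 5. The imbalance rule.** Adding covariates that differ at baseline (t test, p<0.05) changed the model in 25-41% of simulated trials and left type I error at 4-6%.

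**The case against.** The strongest reply is that the primary comparison is already named. The plan states one main hypothesis and a fixed covariate list, neither written as conditional on the interaction step, and no sentence lets a within-stratum result carry the hypothesis. If the stratified final analysis means adjustment for strata, which is the natural reading where the plan stratifies for fall history, type I error stays at 4-6% and power is kept. The trial is also a pilot, and the FSST means and SDs needed to power a later trial are computed whatever happens.

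Much of this stands. A reader might infer that the trial's type I error is 23-30%. The documents do not support that, because the figure needs both one-at-a-time testing and a claim rule that they never state. A reader might also infer that there is no trigger at all; there is one, significance in the model, though it is not operational. The imbalance rule does no type I harm. The reference to logistic regression is best read as a slip, since the outcome is a time in seconds.

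What does not stand is that the text is therefore safe. A stratified analysis adopted because effect modification has been declared is just as naturally read as separate results by stratum. The fall-history stratum is fixed in advance; this rule ranges over all covariates and depends on the data.

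**Conclusion.** The point holds as a should-fix. The plan contains a data-driven switch away from its own primary model, without multiplicity control and without saying which result decides. With no true effect modification, the switch would fire in about a third of trials or somewhat more on two plausible readings, and in about 5% on the mildest.

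The effect on type I error is conditional: none of note if a pooled stratum-adjusted estimate decides, and 23-30%, 11-20% or 6-8% (one at a time, any term in a joint model, single joint test) if a within-stratum result may support a claim. The false subgroup message under a uniform effect is the more general harm, because it arises whenever stratum results are reported as the final analysis. All these figures rest on 46 completers, ten covariates and the assumed splits and correlations above.

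A reader might also infer that the analysis plan is to be completed after unblinding. The Blinding and Unblinding Plan describes the merge of the allocation list, the database lock and the finalising of the analysis plan at study end, but does not say whether finalising comes before or after the merge. It therefore offers no safeguard, but it does not show a breach.

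**What to change.** - State that one linear ANCOVA of 12-week FSST (or change) on arm, baseline FSST, fall-history stratum, age, gender and race, under the plan's intention-to-treat principle, gives the single pooled treatment effect that decides the primary hypothesis.
- Delete the sentence that makes the final analysis stratified. Label interaction and subgroup results exploratory, never replacing the pooled estimate.
- Take covariates from this fixed list rather than from baseline significance tests. This is a tidy-up, since type I error is about 4-6% either way.
- Replace logistic with linear.
- Fix the model in the protocol now, or finalise the analysis plan before any outcome data are viewed by arm. Sign-off before the merge is not enough by itself, because the statistician issues the assignments and handles the randomisation list.

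The cost is wording and the timing of sign-off, with no new data and no change in sample size. The downside is that a real effect modifier would be reported only as exploratory. The change does not settle how missing 12-week FSST values are handled among the 55 participants to be recruited; that needs its own statement.
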